## VII. Appendix 1: Table of Procedures in Longitudinal Protocol

Minimum Procedure Set	Characterization			Longitudinal Follow-up						Long-term Extension		
	Baseline	Steroid Responsiveness		6 mos 	12 mos	18 mos 	24 mos	30 mos 	36 mos	Annual PC 	Annual clinic visit	
	V1 	V2 (pre)	V3 (post)		V4		V5		V6		V7	V8-V9
Visit scheduling window (6 month to V6 calculated from time of enrollment)		Max BD must be w/in 6 weeks of V2	18 ± 3 days from V2	6 mos ± 60 days	12 mos ± 90 days	18 mos ± 60 days	24 mos ± 90 days	30 mos ± 60 days	36 mos ± 90 days	± 60 days	48 mos ± 90 days	± 90 days
Consent and eligibility	X											
SARP 3 Questionnaires	X			X	X	X	X	X	X	X	X	X
Validated questionnaires 	X	X	X	X	X	X	X	X	X	X	X	X
Physical exam/VS/Hgt/Wgt/BMI	X				X		X		X		X	X
Tanner staging												
Spirometry	X	X	X		X		X		X		X	X
Max bronchodilation	X 	X 	X		X		X		X		X	X
Methacholine	X 											
Urine pregnancy test	X	X	X		X		X		X		X	X
Urine collection		X	X		X		X		X		X	
Sputum induction (ages 12 and above)		X	X		X							X
Exhaled nitric oxide		X	X		X		X					X
Exhaled breath condensate		X	X		X		X		X			X
Blood sample – CBC		X	X						X		X	X 
Blood sample – DNA / RNA (Paxgene)		DNA	DNA						RNA			Both 
Blood sample – Serum, plasma		X	X		X		X		X		X	X 
Blood sample – HbA1c, cholesterol, HDL, triglycerides, glucose (fasting), insulin (fasting)									X			
ImmunoCap (includes IgE)		X										
Corticosteroid treatment 		X										
Online Asthma Exacerbation Ques.	Monthly or as exacerbations occur											

Testing in V1 may be completed on several days as determined by individual site standard operating procedures. Specific Validated Questionnaires are detailed in the MOP.

Maximal reversibility must be completed within 6 weeks of V2, either at V1 or V2. It must be repeated at V2 if medications change after V1 procedure. Adults who do not reverse ≥12% for study qualification may additionally be given 4 puffs ipratropium bromide MDI, with spirometry repeated 30 minutes later. Methacholine challenge will be performed only if subject does not have a previously positive methacholine challenge (as defined in MOP). Treatment administered at end of visit 2. Subject contact by telephone only (PC=Phone Call). At either Visit 8 or Visit 9.

## **VIII. PLANNED ANCILLARY PROCEDURES**

The longitudinal protocol is designed to comprehensively characterize all subjects with specific focus on clinical variables (questionnaires), lung function (bronchodilator reversibility), corticosteroid responsiveness and collection of shareable biospecimens for use in mechanistic studies. Sites will endeavor to collect all information and samples that are part of the core longitudinal protocol on all SARP subjects. Each site, however, has independent specific aims and mechanistic studies that have been peer reviewed by a NHLBI Special Emphasis Panel and require additional evaluations on a subset of subjects, either at their sites or at several (but not all) sites. These procedures will be superimposed on the parent longitudinal protocol, but will not interfere with that protocol per se. Attached is a study grid detailing which procedures are anticipated to occur at which sites and the estimated timing of these ancillary procedures in the parent longitudinal protocol. The Manuals of Procedures (MOP) for any procedures that are being conducted at more than one site are incorporated as sections in the SARP MOP accompanying the longitudinal protocol. These procedures will be performed in a consistent manner among sites performing similar assessments. Below are brief excerpts from the grant applications of the seven clinical sites that summarize the hypotheses and aims of the planned mechanistic studies. The ancillary procedures proposed by the sites are designed to explore these hypotheses.

### **SPECIFIC AIMS FROM CLINICAL CENTERS**

#### **Brigham and Women's Hospital (Boston)**

#### **“AMSA: ALXR/FPR medicated signaling in severe asthma”**

The proposed experiments will test the hypothesis that ALX axis dysregulation underlies persistent asthma and airway inflammation despite corticosteroid therapy in a cohort of patients with severe asthma. Lipoxin A4 (LXA4) is an anti-inflammatory and pro-resolving mediator that can interact with specific receptors (i.e., ALX/FPR2) to inhibit allergic airway inflammation and hyper-responsiveness in model systems. Severe asthma is characterized by decreased LXA4, suggesting that this condition may stem from a defect in counter-regulation. To test our hypothesis, we propose two principal specific aims: 1. Determine the effect of corticosteroids on the ALX axis in severe and non-severe asthma, and 2. Define the relationship between the ALX aberrant phenotype and airway inflammation and progressive disease. The long-term goals for this research are to develop a comprehensive understanding of the perturbations in the ALX axis to the pathogenesis of severe asthma and the potential for components of this axis (lipoxins in particular) as possible novel therapeutic agents to alleviate severe asthma's excess morbidity.

#### **University of Pittsburgh**

#### **“Implications and stability of clinical and molecular phenotypes of severe asthma”**

Published SARP II data show that chymase positive mast cells (MCTC) predominate in the submucosa and epithelium in severe asthma, with evidence for an altered activation status.

Preliminary data suggest that a luminal MCTC mRNA signature and activation pattern even better differentiates symptomatic and exacerbation prone severe from milder asthma. This MC signature is present across at least 2 of the 3 predominant severe asthma clusters. However, the mechanisms behind these changes, the interaction of these MCs with epithelial/inflammatory cells and their long term effects (and stability) are poorly understood. The goals of this application are to establish a longitudinal protocol capable of identifying asthma phenotypes and their long term implications in both adults and children with asthma and severe asthma, as well as evaluating their stability. This longitudinal protocol will intersect with mechanistic studies which identify a MCTC molecular phenotype, relate it to genetic characteristics as well as short/long term cellular, clinical, physiologic and radiologic outcomes and then analyze its stability over time. Finally, the proposal will mechanistically determine the impact of this mast cell signature on human airway epithelial cells. This innovative combination of in vitro/in vivo mechanistic and longitudinal molecular and clinical phenotyping is highly likely to uncover new molecular targets for severe asthma.

**University of California San Francisco**  
**“Clinical and molecular phenotypes of severe asthma”**

Our overarching hypothesis is that differences in clinical presentation, outcomes, and response to therapy in severe asthma are driven by: 1) distinct types of airway inflammation and remodeling developed and maintained by specific molecular pathways; 2) microbial colonization or infection; 3) genetic/epigenetic factors. Aim 1 proposes a shared longitudinal protocol to identify and validate phenotypic characteristics of severe asthma based on underlying pathobiology and pathophysiology. Aim 2 will explore mechanisms of pathologic mucus in severe asthma in two sub-aims that will both use rheology to quantify the viscoelastic properties of induced sputum from patients with chronic severe asthma. We will identify subgroups of severe asthmatics with chronic mucus hypersecretion and abnormal mucus rheology, determine the clinical and biological characteristics of these subgroups, and explore in ex vivo studies the role of multimeric lectins as cross-linkers of mucin polymers and potential targets of glycomimetic therapy. Included in the lectins we will study will be *Aspergillus fumigatus* lectin, a fucose binding lectin that we hypothesize to have a pathogenic role in the mechanism of mucus plug formation in Allergic Bronchopulmonary Aspergillosis, an important subtype of severe asthma.

**University of Virginia/Cleveland Clinic**  
**“Airway redox biochemistry as a determinant of asthma phenotype during adolescence”**

Through innovative metabolomics and redox biochemistry, methodologies that are a strength and unique to our collaborative efforts, we identified clinically relevant phenotypes of asthma. The phenotypes are defined by biomarkers specific to underlying biochemical mechanistic abnormalities, including eosinophil-mediated oxidation, depletion of antioxidants and protective airway S-nitrosothiols, and airway acidification. Here, we propose to study a new component that is informative for longitudinal assessment of severe asthma phenotypes: gender effects. We reason that identification of the metabolic mechanism(s) underlying onset of severe asthma

in young women during adolescence, and resolution of severe asthma in boys, will reveal fundamental pathophysiology of severe asthma. Importantly, we aim to develop clinical testing procedures to accurately assign metabolic asthma phenotypes; and to follow patients in each phenotype to uncover clinical longitudinal outcomes. At the conclusion of the project, we anticipate that we will have 1) developed clinically relevant tests to identify severe asthma phenotypes; 2) determined the longitudinal outcome of the phenotypes; and 3) identified the mechanisms underlying the preponderance of women in the severe asthma population. This application will focus on the development of clinically relevant metabolic tests to identify subphenotypes of adults and children with severe asthma and will lead to new targeted innovative treatments.

#### **Wake Forest School of Medicine**

#### **“Longitudinal phenomics and genetics of severe asthma”**

We hypothesize that 1) an important cause of severe asthma is altered inflammatory responses that are partially related to sequence variants in genes that regulate bronchial inflammation, pulmonary function or affect structural components in the airways and 2) a subset of patients develops severe asthma because of pharmacogenetic responses to pharmacologic agents. Our first aim is to understand the longitudinal characteristics that are important in the development of severe asthma using both standard and cluster approaches. An evoked phenotype will be assessed two weeks after administration of triamcinolone acetonide injectable suspension by evaluating changes in baseline phenotypes including lung function, bronchial responsiveness, induced sputum and biomarkers. A subset of subjects will undergo investigative bronchoscopy at baseline and following corticosteroid treatment as part of the evoked phenotype assessment. Our second aim is to determine genetic and biomarker predictors of baseline phenotypes and their change over time. New subjects will be assigned to a current SARP asthma cluster. When the total population has been studied, a new cluster analysis will be performed for comparison with the current clusters, including additional biomarkers and CT imaging. Individual changes in cluster assignment will be assessed longitudinally. Biomarker and genetic analysis (including the role of rare variants) will be performed using the clusters and longitudinal data including lung function, as well as pharmacogenetic analysis of the evoked systemic steroid phenotype.

#### **Washington University**

#### **“Molecular basis and structural and physiologic consequences of airway remodeling in severe asthma”**

The overall goal of this proposal is to better understand the molecular basis and structural and physiologic consequences of airway remodeling in severe asthma and how remodeling changes over time. We propose that individuals with severe asthma, in comparison to well controlled asthma, have: (I) increased airway remodeling as evidenced by goblet cell metaplasia and mucin production, (II) greater airway thickness by multidetector-row CT of the chest (MDCT) leading to ventilation defects demonstrated by hyperpolarized helium ( $^{3}\text{He}$ ) MRI and air trapping demonstrated by MDCT, and (III) airway remodeling associated with more severe and progressive airflow obstruction. We hypothesize that the goblet cell metaplasia and increased

mucin we have observed in severe asthma are being driven by an IL-13- and EGFR-dependent mechanism that inhibits epithelial cell apoptosis and allows IL-13 differentiation of the airway epithelium into goblet cells (Aim I). We further hypothesize that this remodeling of segmental airways in severe asthma leads to distal ventilation defects and air trapping (Aim II). In an effort to define potential predictors of subsequent decline in lung function in severe asthma, we hypothesize that baseline airway remodeling as reflected by MDCT airway wall area (AWA%) is predictive of FEV1 (post-corticosteroid/bronchodilator FEV1) decline (Aim III). The identification of potential variables associated with remodeling and severe asthma will help identify individuals at risk who would benefit from specific targeted therapy.

**University of Wisconsin**

**“Stability of severe asthma phenotypes: impact of exacerbations”**

We have shown that patients with severe asthma have more extensive air trapping compared to those with non-severe asthma. Airway imaging has shown increased heterogeneous regional ventilation defects and air trapping. Some of these defects are persistent, while others can be provoked with virus-induced exacerbations or bronchial challenge and recur in the same general areas on repeated challenge, suggesting localized airway dysfunction. In preliminary studies, inflammatory parameters tended to be more prominent in segments that showed ventilation defects on imaging. In other studies, we showed that children with recurrent severe wheezing episodes have lower lung function later on, an observation supported by published studies on adult and pediatric patients with asthma. Therefore, we hypothesize that severe asthma exacerbations, in some patients, are associated with incomplete recovery and activation of airway inflammatory cells in a regional distribution. This leads to enhanced airway injury with airway dysfunction as reflected by ventilation defects and air trapping, and a more generalized increase in disease severity. To evaluate this hypothesis we propose the following specific aims:

1. To refine phenotyping of severe asthma using new variables from multiple domains in a large longitudinal patient cohort; and to determine the contribution of severe asthma exacerbations to disease progression.
2. To characterize regional obstructive patterns at baseline and their relationship to changes in pulmonary function; and to determine how incremental changes in regional airway dysfunction after recovery from asthma exacerbation may contribute to severe asthma.
3. To determine the contribution of established and novel biomarkers (YKL-40, vWF, & P-selectin), in refining the severe asthma phenotypes and the role of inflammatory cells in causing airway injury following virus-induced asthma exacerbations with subsequent development of ventilation defects.

## Appendix 2: TIMING OF PLANNED ANCILLARY PROCEDURES AT CLINICAL SITES

	Characterization					Longitudinal Follow-up								Extension			Exacerbation 	
	Baseline		Steroid Responsiveness			phone	V4	V4a	phone	V5	phone	V6	V6a	V7	V8	V9	EV1	EV2
	V1	V2	V2a	V3	V3a													
LONGITUDINAL PROTOCOL	X	X		X		X	X		X	X	X	X		X	X	X		
Corticosteroid treatment			X 															
Lung volumes and/or DLCO	C Wis				Wis			C Wis		C Wis		C Wis		Wis				
Additional EBC							P		P		P Wis			B WU	B WU	Wis		
Additional Blood for biomarkers	VA/C	VA/C		VA/C			VA/C		VA/C WF		VA/C WF Wis		VA/C WF Wis	B VA/C WF Wis	B VA/C WF Wis	P SF WU Wis	P SF WU Wis	
Additional Urine														C	C			
CBC														B SF	B SF			
FeNO									SF VA/C WF WU		C			B P C	B P C	P SF WU Wis	P SF WU Wis	
Additional Sputum Induction	SF 	B		B			B		P SF VA/C WF Wis		B P SF VA/C WF Wis			WF WU SF	WF WU SF	P SF WU Wis	P SF WU Wis	
Nasal Sampling (lavage, swab, blow) 	VA/C Wis						P SF WU Wis		P SF VA WU Wis		VA Wis					P SF WU Wis	P SF WU Wis	
Stool Sample										P B Wis SF WU 		P B Wis SF WU 						
CT imaging	P SF C WF Wis	B WU								B P SF C WU Wis								
MRI imaging	Wis	WU								Wis							WU Wis	
Bronchoscopy	Wis		P SF WU				C 	C			C	WU						WU Wis
Bronchoscopy Steroid Protocol 			B C WF		B C WF													

**Boston (B); Pittsburgh (P); UCSF (SF); UVa/Cleveland Clinic (VA/C); Wake Forest (WF); WashU (WU); Wisconsin (Wis)**

In the subset of subjects undergoing bronchoscopy, corticosteroid administration will be delayed until after bronchoscopy has been performed.

Four sites will perform exacerbation visits with acute assessments and convalescent follow-up.

UCSF will perform a second sputum induction for rheologic measures 48 hours after scheduled longitudinal protocol sputum inductions.

UVa/Cleveland will perform paired bronchoscopies (3 months apart) in subset of women to evaluate hormonal changes in the airways.

Three sites will perform paired bronchoscopies (21 days apart) in a subset of subjects, before and after parenteral corticosteroids

Nasal brushings obtained in a subset of participants at V4, V5 or V6, with additional samples for some participants at EV1 and EV2.

Stool samples obtained in a subset of adults at V6, V7, or V8

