**Sputum Induction.** Sputum cells and fluid phase will be saved for assessment of lower airway inflammation and presence of respiratory pathogens. The following safety procedures will be followed for the sputum induction procedure; all subjects will be pre-treated with 4 puffs of albuterol pre-induction and only subjects (aged 12 and above) with a post bronchodilator FEV1 of >50% predicted (>70% in children aged 12 to 17 years) will undergo sputum induction. Spontaneous sputum samples may be collected on subjects with an FEV1 below these limits. A physician will be available during the challenge; study staff will calculate and record the peak flow and FEV1 value that equals both a 10% and 20% fall in lung function based upon the recorded post-bronchodilator peak flow and FEV1 values and subjects will not be discharged until their FEV1 is within 10% of their post bronchodilator FEV1 (see Sputum MOP).

**Corticosteroid administration.** Each subject that meets inclusion/exclusion criteria will receive triamcinolone acetonide intramuscularly at the end of visit 2. Adults  $\geq 18$  years will receive 40 mg triamcinolone acetonide. Children 6-17 years will receive 1 mg/kg triamcinolone acetonide (up to 40 mg maximum). Triamcinolone acetonide will be administered as a single intramuscular dose deep in the gluteal region. Visit 2 will be timed so that the triamcinolone injection is not given within 4 weeks of the administration of any live attenuated vaccine.

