### **Visit 2 – Approximately 2.5 hrs**

At this visit, blood will be drawn for CBC with differential count, total IgE, ImmunoCap and isolation of DNA for SARP genetic studies to evaluate genes that may be related to the development of asthma, allergy and related diseases. Plasma and serum will be processed and saved for analysis. A urine specimen will be obtained from each individual for assessment of oxidative metabolites. Females of childbearing potential will have a urine pregnancy test. A brief medical history, adverse event and concomitant medication update will be conducted. The ACQ questionnaire will be administered. If pre- and post-albuterol spirometry has not been completed within the previous 6 weeks, or if the subject's medications have been changed since it was last done, it will be performed at this visit. In addition, a sputum induction will be conducted to evaluate airway inflammation on subjects age 12 and above. Exhaled nitric oxide will be measured, and exhaled breath condensate will be collected. After all procedures have been completed at this visit, subjects will then receive a single intramuscular injection of triamcinolone acetonide. If a procedure cannot be completed as planned, the injection should be rescheduled following the completion of the required procedures.

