### **Visit 3 – Approximately 2.0 hrs**

This visit will be a repeat of procedures already completed and will occur within 18 days ( $\pm$  3 days) post Visit 2. These procedures include spirometry, maximum bronchodilation, a brief medical history, ACQ, adverse event and concomitant medication update, blood draw (for CBC with differential count, isolation of DNA for SARP epigenetic studies, plasma, and serum), urine and sputum (ages 12 and above) will be collected, exhaled nitric oxide will be measured, and exhaled breath condensate will be collected.

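### Does delaying the steroid injection in the bronchoscopy subset leave Visit 3 at the wrong time after the drug?

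*Combined protocol and SAP*

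**What the plan says.** **Injection time, core protocol.** Section III.C: "Each subject that meets inclusion/exclusion criteria will receive triamcinolone acetonide intramuscularly at the end of visit 2". Appendix 1, footnote 5, agrees: "Treatment administered at end of visit 2". The vaccine rule in III.C also treats the visit and the injection as one date: "Visit 2 will be timed so that the triamcinolone injection is not given within 4 weeks of the administration of any live attenuated vaccine".

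**Injection time, exceptions.** Appendix 2, footnote 1: "In the subset of subjects undergoing bronchoscopy, corticosteroid administration will be delayed until after bronchoscopy has been performed". Separately, Section III.D, Visit 2, covers any participant whose visit is incomplete: "If a procedure cannot be completed as planned, the injection should be rescheduled following the completion of the required procedures".

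**Visit 3.** Appendix 1 sets the window at "18 ± 3 days from V2". Section III.D, Visit 3, also counts from Visit 2: "This visit will be a repeat of procedures already completed and will occur within 18 days", with a tolerance of 3 days either way.

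**Other timing statements.** In Section VIII, the Wake Forest grant excerpt counts from the drug: "An evoked phenotype will be assessed two weeks after administration of triamcinolone acetonide injectable suspension". Appendix 2, footnote 5, puts paired bronchoscopies at three sites 21 days apart, before and after the steroid. Section VIII also says that ancillary procedures are laid over the core protocol without disturbing it, and that those done at more than one site are covered in the Manual of Procedures.

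**Analysis.** Hypothesis 3 uses the change in sputum cell profile with corticosteroid therapy to find severe-asthma subgroups at risk. Section III.J names kinds of covariates by example and does not mention days since injection.

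**The concern.** Counting Visit 3 from Visit 2 equals counting from the drug only while the two share a date. Footnote 1 separates them for some participants, and no passage in the protocol ties them together again. The Appendix 2 grid, as it appears in the text available to us, lists bronchoscopy under V2a at six of the seven centers, so this would not be one site's habit.

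If the injection came days after Visit 2 and Visit 3 stayed put, the steroid response would be read sooner after the drug in bronchoscopy participants than in others seen on the same Visit 3 day. That shift would be systematic. Adjusting for clinical center would not remove it, because bronchoscopy participants are a subset within a center. What is at stake is the comparability of the Visit 2 to Visit 3 change used for Hypothesis 3.

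**Working it through.** **Inputs.** Visit 3 window: 18 ± 3 days from Visit 2, so days 15 to 21 (Appendix 1; Section III.D). Delay from Visit 2 to injection: *d* days. The documents give no value for *d*, so it is an assumption, shown from 0 to 3 days.

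**The plan's own case.** With the injection at the end of Visit 2, *d* = 0, and Visit 3 falls 15 to 21 days after injection, nominally 18.

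**If Visit 3 stays counted from Visit 2.** Days since injection = (15 to 21) − *d*.

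| *d* | Days since injection | Nominal | Window days earlier than 15 after injection |
|---|---|---|---|
| 0 | 15–21 | 18 | 0 of 7 |
| 1 | 14–20 | 17 | 1 of 7 |
| 2 | 13–19 | 16 | 2 of 7 |
| 3 | 12–18 | 15 | 3 of 7 |

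**If Visit 3 moves with the injection.** The interval is 15 to 21 days for every *d*, and there is nothing to correct.

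**Room inside the written window.**
- A Visit 3 exactly 18 days after injection falls on day 18 + *d* from Visit 2. It is in window when 18 + *d* ≤ 21, so *d* ≤ 3.
- The latest in-window Visit 3 is 21 − *d* days after injection. It still reaches 15 days when 21 − *d* ≥ 15, so *d* ≤ 6.

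**Comparison with the spread already accepted.** If Visit 3 days are spread evenly over the 7 allowed days (an assumption), their SD is √((7² − 1)/12) = √(48/12) = 2.0 days. A 2-day delay would therefore move the bronchoscopy group by one SD of the spread that the design tolerates in everyone.

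**Is *d* likely to be large?** The text suggests that the injection is meant to close Visit 2:
- Section III.D, Visit 2, gives it after all of that visit's procedures, and reschedules it until they are done.
- Appendix 1 labels Visit 2 as pre and Visit 3 as post under steroid responsiveness.
- The vaccine rule times Visit 2 by the injection.
- In the Appendix 2 grid the only corticosteroid mark is under V2a. It has to serve everyone, including those without bronchoscopy who are injected at the end of Visit 2, so V2a need not mean a later day.

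The grid cannot carry more weight than that. In the text available to us, some later entries put bronchoscopy and sputum induction under telephone contacts, so columns have evidently shifted.

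**The other two intervals.** The 21 days in footnote 5 separates two bronchoscopies and does not anchor Visit 3. The two weeks in the grant excerpt (14 days) is one day below the *d* = 0 range and may be shorthand.

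**The case for a change.** The best case for a change is that the gap is in the words and does not depend on the grid. Footnote 1 says the injection is delayed, Appendix 1 counts from the visit, and nothing joins the two. The statement that ancillary work leaves the core protocol undisturbed gives no rule for Visit 3. Any shift would follow bronchoscopy status, and the remedy is cheap: one sentence of wording and one derived variable.

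The textual point stands. The passages on injection time and on the Visit 3 window do not fit together for the subset, and if the text is reopened they should be reconciled on what the window is counted from. This review takes no position on which timing is right.

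The step from there to a needed change does not stand:
- The delay, the size of the subset and the course of the response between days are all unstated, so no bias can be computed.
- Section V describes the Manual of Procedures as covering the study from screening through to statistical evaluation. An anchor date for an ancillary subset is the kind of detail it would hold.
- Section III.J fixes no covariate set for any single hypothesis. Not naming this interval is therefore no special omission, and the section permits its use.
- Hypothesis 3 relates sputum change to later risk and does not compare bronchoscopy with non-bronchoscopy participants. A shift would matter only if bronchoscopy status were also related to risk, or if the response changed appreciably over the days concerned.
- This is version 12.0 of 10/16/2019, so most Visit 3 data have probably been collected. New scheduling text would hardly change them.

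**Conclusion.** No change is needed. The documents leave unwritten what the Visit 3 window is counted from when the injection is delayed, which is a gap in detail rather than a flaw in the design. At a delay of 0 there is no effect. At 1 to 3 days the interval moves by that many days if Visit 3 stays fixed, and a site can offset the whole shift by booking Visit 3 later within the existing window. If Visit 3 follows the injection, there is no shift at any delay.

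This rests on two things the documents do not confirm: that the delay is short or zero, as the text on Visit 2 suggests, and that the injection date is recorded. If it is, an analyst of the steroid response would tabulate days from injection to Visit 3 by bronchoscopy status and use the interval as a covariate only if it differs. Section III.J already leaves room for that. A delay of more than 6 days with Visit 3 held fixed would weaken this conclusion, because no in-window visit would then reach 15 days after injection. Nothing in the documents points to such a delay.
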